5.2 Patients and Families: Inclusion and Exclusion Criteria for Patient Subjects

Potentially eligible patients are logged for study enrollment at the time the medication alert fires. Patients are assigned to the study arm of the randomized prescribing provider. Local study staff will blindly confirm eligibility via medical record review for all intervention and control arm patients logged for eligibility review and enrollment.

Inclusions:

- Patient is ≥ 3 and < 18 years of age at the time of the encounter at which the study alert fired;
- Study service (BH navigation, bridging therapy, CAP consult) ordered in Epic for the patient;
 - The BPA allows providers to remove the antipsychotic order and still order services.
- Patient is initiating a new episode of outpatient treatment with an antipsychotic medication.
 - New episodes are defined by no record of an antipsychotic medication being ordered within the health system as part of an outpatient care plan in the prior 180 days.

Exclusions:

- Patient has a diagnosed psychotic disorder, mania, autism spectrum disorder, or intellectual disability;

- Patient was enrolled in the SUAY pilot study;
- The antipsychotic entered is prochlorperazine (Comazol®) – which is used to treat nausea;
- An outpatient antipsychotic order is entered by a temporary provider in the health system. For example, a “doc of the day” signing an order initiated by a pharmacist transferring an existing prescription to the health system. This situation may also occur when a temporary provider signs a medication order for a prescription initiated in an inpatient setting as part of a discharge plan.
 - Note that orders placed by temporary providers do not count towards the 180 day medication free period for defining a new episode of care.
- The antipsychotic order was placed within an urgent care, emergency department, or inpatient setting (to avoid intervening during a crisis).
 - Note that orders placed in these settings do not count towards the 180 day medication free period for defining a new episode of care.
- Primary language is not English (e.g., patient requires a translator).

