All primary analyses will follow an intent-to-treat approach, including all individuals assigned to an intervention arm regardless of the amount of intervention received. Non-inferiority evaluations will also be evaluated in a supplementary “as treated” analysis, comparing outcomes according to treatments actually received by patients during their observed period of follow-up. This supplemental comparison is useful in a non-inferiority assessment due to the fact that the alternative hypothesis of “no effect” is more likely in the presence of protocol violations and therefore the intent to treat approach will be anti-

conservative if many patients in the intervention arm, for example, revert to control. Also, non-inferiority of Emergency Department visit rate in the intervention arm compared to usual care control will only be assessed on final analysis if superiority is shown for the primary endpoint of no antipsychotic use at 6 months.

We will use Poisson regression to estimate (1) the percent of individuals using antipsychotics at 6 months post enrollment and (2) the total number of person-months of antipsychotic use by youth in the six month follow-up period, per provider medication orders, in each of the study arms. We will use generalized estimating equations(43) to estimate the parameters in the Poisson regression model. We will use the robust sandwich estimator to ensure correct standard errors for the intervention effect due to possible violation of the Poisson variance assumption(44); additionally, this will allow us to account for any clustering within clinics(43) and providers. Poisson regression allows comparison of relative incident rates among the intervention arms when outcomes are not rare(45). Additionally, Poisson regression will allow us to control for pre-specified baseline covariates (age, gender, and race) as well as site differences in any antipsychotic use and allow for straightforward estimation of site-specific intervention effects in sensitivity analyses. For a secondary analysis, we will repeat this approach defining antipsychotic use with prescription fill data rather than orders.

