Data for our primary outcome of interest, any antipsychotic use, will be collected from electronic health records on provider orders. Electronic health record data on prescription fills will be used to assess the secondary outcome (antipsychotic medication fills). This means that traditional study drop-out due to premature participant withdrawal from the study will not lead to missing data in primary analyses. However, there will be the potential for differential follow-up rates among individuals due to youth disenrolling from their or their parent/guardian's health plan. Death is also a possibility, but unlikely. We will compare those youth for whom we are only able to collect outcome information for a portion of the 6 month follow-up period to those participants for whom we have complete 6 month follow-up information on their demographics, treatment group, and other salient baseline variables. We will account for differential follow-up times due to disenrollment in the Poisson regression model using an offset(46). Because our power calculations are based on excluding all individuals lost-to-follow-up due to disenrollment, these estimates are conservative.

The secondary outcome of emergency department visits will be estimated by Poisson regression in each of the arms, again using generalized estimating equations for the reasons listed above for the primary outcome. The intervention will be compared for non-inferiority to control using a margin of $M=1.5$. This margin of 1.5 for the rate ratio represents a threshold for the relative increase of 50%, beyond which we would consider unacceptable. Sikirica (2014) observed an annual rate of 0.39 per year among adolescents with attention deficit/hyperactivity disorder who were taking antipsychotics(47). Using an estimated rate of emergency department visits of 0.0325 per month on control(47), the non-inferiority margin of 1.5 for the incidence rate ratio would represent a corresponding maximum acceptable rate of 0.0488 per month in the intervention arm. If the rate of emergency department use is greater than expected, say 0.05, then the non-inferiority margin of 1.5 would correspond to a maximum rate of 0.075 in the intervention arm. The estimated treatment effect (emergency department rate on algorithm

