divided by the rate on control, estimated by Poisson regression) and 95% two-sided confidence interval (CI) will be compared to the non-inferiority margin (overall: $M = 1.5$) and non-inferiority of the algorithm approach will be declared if the entire coverage of the 95% CI is less than 1.5.

In safety review reports, the ratio between arms of emergency department visit rates will be accompanied by a confidence interval and by the non-inferiority margin, 1.5, for reference. Confidence intervals will be defined by estimating the rate ratio in 5,000 bootstrap samples. Resampling will be done on the cluster (provider) level and stratified by the presence of any event within each cluster. Quantile-based confidence intervals will be identified using the appropriate percentile corresponding to the Pocock alpha-spending function for interim analyses. Excess harm is observed if the entire coverage of the confidence interval for the rate ratio comparing the greater to the lesser rate of emergency department and urgent care visits is greater than 1.5. (While the final non-inferiority analysis for this safety outcome will use the robust sandwich estimator to ensure correct standard errors, the properties of this estimator are based on asymptotic behavior and small sample size performance may be poor.)

We anticipate initial follow-up of 800 patients, randomized to the two arms, with 720 patients remaining enrolled in the study at 6 months of follow-up (i.e., 10% lost to follow-up). Assuming a $P < 0.05$ alpha level, and based on an anticipated 95% of patients in the control arm using antipsychotics at 6 months, this sample will ensure over 95% power to detect a 6% reduction in the percent of participants with any order for antipsychotic medications at 6 months. Furthermore, we expect to have 80% power to detect a 13% reduction in subgroups with exposures occurring with 25% prevalence, and 80% power to detect a 17% reduction in subgroups with exposures occurring with 18% prevalence (e.g., racial/ethnic minorities). A minimal clinically important difference of 10% was pre-specified to allow for evaluation of clinical significance as well as statistical significance. We have over 90% power to detect a 10% reduction in antipsychotic use at 6 months for patients in the intervention arm given a rate of 85%, 90%, or 95% use in the control arm.

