As these power calculations are based on the assumed percent of participants on any antipsychotic in the control arm and assumed pattern of intervention effects, we provide examples of detectable intervention effects corresponding to alternative scenarios in the table that follows, including varying rates of subgroup prevalence to evaluate power regarding intervention effectiveness in less prevalent minority groups. In summary, at a range of percentages of participants with any antipsychotic use in the control arm, we will have excellent power to detect a variety of clinically meaningful intervention effects within the expected range.

Using an estimated rate of emergency department visits of 0.0325 per month on control(47) and with a one-sided 0.025 alpha level with equal allocation between groups, we estimate 71% power(48) with 400 patients per arm and 67% power with 360 patients per arm (allowing for loss to follow-up) respectively, to detect equality of emergency department visit rates (i.e., a true rate ratio of 1) in a non-inferiority evaluation with a margin of 1.5. With a greater monthly emergency department rate of 0.05, we would have 88% and 84% power with 400 and 360 patients per arm respectively under otherwise equivalent conditions.

Power under varying percentages of participants in each arm taking antipsychotic medication at 6 months (based on medication orders) and under various subgroup prevalence assumptions.

Subgroup prevalence	n per arm*	Intervention	Control	Power
100%	360	89%	95%	80%
100%	360	85%	95%	>99%
100%	360	80%	90%	97%
100%	360	75%	85%	92%
25%	90	82%	95%	80%
18%	65	78%	95%	80%
10%	36	75%	95%	67%
5%	18	65%	95%	62%

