Inferential analysis for this outcome will estimate **the odds ratio (OR) of AP use observed at 6 months** between intervention and control. For this analysis, we will use a logistic regression model where the outcome is a binary indicator of AP use observed at 6 months. Binary treatment arm assignment and any inpatient hospitalization in the prior year will be the only covariates

Analysis plan for Safety Use of Antipsychotics in Youth (SUAY)

included in the regression model. The estimated coefficient associated with treatment is interpreted as the log-OR of observing AP use at six months for an intervention patient vs. a control patient. Patient is the unit of analysis, GEE will be used to account for correlation within provider, and robust standard errors (with working independence covariance matrix assumed) will be calculated to construct a 95% CI around the estimated OR. Our null hypothesis is that the OR is equal to 1, corresponding to no statistically significant difference between AP use observed at 6 months. We will reject the null hypothesis if the lower bound of the 95% CI is above 1 (increased use in treatment arm) or the upper bound is below 1 (decreased use in treatment arm).

Variables	Definition	Present/Absent
taking_at_6mon	Using AP at 6 months (No (0)/Yes(1))	present
groupn	Randomization Group - use for descriptive stats (Intervention (1)/Control(2))	present
group_cat	Randomization Group - use in models (Control (0)/Intervention (1))	present
prior_hosp	Prior Hospitalization (No (0)/Yes(1))	present

Sensitivity analysis will be conducted using similar approach as mentioned above, we will perform the following separate analyses related to our primary outcome by:

- % of patients taking antipsychotic medications (measured by orders) at 6 months post enrollment, using the minimum based on SIG reviews
- % of patients taking antipsychotic medications (measured by orders) at 6 months post enrollment, using the maximum based on SIG reviews
- % of patients taking antipsychotic medications (measured by prescription fills) at 6 months post enrollment. Note that this analysis may be performed using three healthcare systems (KPWA, KPCO, and KPNW) due to limitation in data availability

Variables	Definition	Present/Absent
taking_at_6mon_min	Using AP at 6 months - minimum (No (0)/Yes(1))	present
taking_at_6mon_max	Using AP at 6 months - maximum (No (0)/Yes(1))	present
taking_at_6mon_fills	Using AP (fills) at 6 months (No (0)/Yes(1))	present

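### The stated powers treat patients as independent although prescribers are randomised; at 85% control use the claim of over 90% fails once the design effect passes about 1.08, and the 89% vs 95% power is given as two conflicting figures.

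*Protocol*

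**What the plan says.** Prescribers are the randomised units (Protocol Précis and section 5.3.1). For patients, section 5.2 states "Patients are assigned to the study arm of the randomized prescribing provider".

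The analysis allows for this. Protocol section 8.2.1 uses the sandwich estimator "due to possible violation of the Poisson variance assumption(44); additionally, this will allow us to account for any clustering within clinics(43) and providers". ED visits are modelled "again using generalized estimating equations for the reasons listed above for the primary outcome", and for the ED intervals in safety reports "Resampling will be done on the cluster (provider) level and stratified by the presence of any event within each cluster". The SAP, Primary analysis I, says "Patient is the unit of analysis, GEE will be used to account for correlation within provider".

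The power statements, also in section 8.2.1, are:

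- For the pre-specified 10-point difference: "We have over 90% power to detect a 10% reduction in antipsychotic use at 6 months for patients in the intervention arm", at control use of 85%, 90% or 95%. The table gives 92%, 97% and >99% with 360 per arm, and its rows show that the 10% is an absolute difference.
- For the smaller effect, from 95% control use: "this sample will ensure over 95% power to detect a 6% reduction in the percent of participants with any order". The table row for 89% vs 95% gives 80%.
- For ED non-inferiority at 0.0325 visits per month: "we estimate 71% power(48) with 400 patients per arm and 67% power with 360 patients per arm". At 0.05 per month the figures are 88% and 84%.

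The stated inputs are the control percentage, the pattern of effects, the ED rate and 10% loss to follow-up. No intracluster correlation (ICC), number of prescribers, cluster size or design effect is given. Sections 8.2.1 and 8.3 call the powers conservative, and the only reason offered is that disenrolled patients are left out.

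**The concern.** When prescribers are randomised, positive correlation between patients of the same prescriber inflates the variance of the arm comparison. Correlation is plausible here because the primary outcomes are built from prescribers' own orders. Section 5.3.1 also reports that at KP Washington a few prescribers wrote a large share of the qualifying prescriptions, and unequal cluster sizes enlarge any design effect. A power computed for independent patients is therefore an upper bound for the planned analysis.

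At stake is what the funder, the DSMB and readers believe the trial can detect, and how they would read a null primary result or a failed ED non-inferiority test. The ED test is reached only if the primary endpoint shows superiority, so it also depends on the primary power.

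**Working it through.** **Formulas**

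Two proportions, pooled variance under the null, two-sided alpha 0.05, n per arm (the protocol gives alpha 0.05 without sidedness; two-sided matches its table):

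power = Φ{ [ |p1 − p2| − 1.96·√(2·p̄(1 − p̄)/n) ] / √([p1(1 − p1) + p2(1 − p2)]/n) }

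ED non-inferiority, margin 1.5, one-sided 0.025, true ratio 1, six-month mean μ = 6 × monthly rate, design effect DE, dispersion k:

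power = Φ{ ln 1.5 / √(2(1/μ + k)·DE/n) − 1.96 }

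**Step 1. Reproduce the plan's figures with no clustering (DE = 1, k = 0)**

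For 75% vs 85%, n = 360: (0.10 − 1.96 × 0.02981)/0.02958 = 1.405, and Φ(1.405) = 92.0%.

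| n per arm | Intervention vs control | Stated | Recomputed |
|---|---|---|---|
| 360 | 89% vs 95% | 80% | **84.5%** |
| 360 | 85% vs 95% | >99% | 99.5% |
| 360 | 80% vs 90% | 97% | 96.5% |
| 360 | 75% vs 85% | 92% | 92.0% |
| 90 | 82% vs 95% | 80% | 78.5% |
| 65 | 78% vs 95% | 80% | 81.7% |
| 36 | 75% vs 95% | 67% | 66.8% |
| 18 | 65% vs 95% | 62% | 62.3% |

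For ED visits at 0.0325 per month, n = 360: μ = 0.195, standard error √(2/(0.195 × 360)) = 0.1688, and 0.4055/0.1688 − 1.96 = 0.442, giving 67.1%.

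| Monthly rate | n per arm | Stated | Recomputed |
|---|---|---|---|
| 0.0325 | 400 | 71% | 71.6% |
| 0.0325 | 360 | 67% | 67.1% |
| 0.05 | 400 | 88% | 88.1% |
| 0.05 | 360 | 84% | 84.6% |

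Eleven of the twelve figures fit independent patients with no overdispersion.

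**Step 2. Design effect at which power for 10 points drops to 90%**

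Find the effective n per arm that gives 90%, then divide it into 360.

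| Control use | Effective n for 90% | Break-even DE |
|---|---|---|
| 95% | 187.0 | 1.92 |
| 90% | 265.9 | 1.35 |
| 85% | 334.2 | 1.08 |

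**Step 3. Translate into an ICC (assumed cluster sizes)**

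DE = 1 + [(1 + CV²)m − 1]·ICC, where m is the mean number of patients per prescriber and CV the coefficient of variation of cluster size. The documents give none of these. Assuming m = 4 and CV = 1.5, the bracket is 3.25 × 4 − 1 = 12. The break-even ICCs are 0.925/12 = 0.077, 0.354/12 = 0.030 and 0.077/12 = 0.006. Over m from 2 to 8 and CV from 0 to 2 the bracket runs from 1 to 39, so the 1.08 limit corresponds to an ICC between 0.08 and 0.002.

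**Step 4. Illustrative power at 360 per arm**

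DE 1.24 and 1.60 correspond to ICC 0.02 and 0.05 with the bracket of 12.

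| Comparison | DE 1 | DE 1.24 | DE 1.60 |
|---|---|---|---|
| 85% vs 95% | 99.5% | 98% | 94.5% |
| 80% vs 90% | 96.5% | 92% | 85% |
| 75% vs 85% | 92.0% | 86% | 76% |
| ED, 0.0325 per month | 67% | 58% | 48% |
| ED, 0.05 per month | 84.6% | 76% | 65% |

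Overdispersion alone (assumed k = 1, DE = 1) gives 59% and 74% for the two ED rates.

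Subgroups lose less, because taking a fraction of each prescriber's patients shrinks the clusters: DE = 1 + prevalence × 12 × ICC under random thinning. At ICC 0.02, 0.05 and 0.10 the 25% subgroup has power 76%, 73% and 67% (stated 80%), and the 5% subgroup 62%, 61% and 60% (stated 62%).

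**Step 5. The row that does not reproduce**

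For 89% vs 95%, n = 360: (0.06 − 1.96 × 0.02022)/0.02010 = 1.013, giving 84.5%. All 400 per arm would give 88.0%, and 95% power needs 529 per arm. The table's 80% would fit a DE of about 1.13 or, roughly, a continuity correction (80.9%). The other 360-per-arm rows fit DE = 1, so this row is not evidence of a clustering allowance. Reading 6% as a relative reduction (95% to 89.3%) makes the effect smaller and the power lower still.

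**The case against.** The strongest reply is that nothing in the inference is wrong: estimates, tests and intervals already allow for within-prescriber correlation, and only planning text would change. That is correct. But robust standard errors do not restore the power that was stated.

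The 85% scenario is also the weakest of the three. The protocol anticipates 95% control use, where the 10-point claim survives to a design effect of 1.92. This stands, but the protocol makes the claim for all three rates.

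The 1.08 limit rests on 360 per arm, whereas the planned analysis keeps disenrolled patients. If all 400 per arm contributed fully, power at 85% control use would be 94.4% and the limit about 1.20; at DE 1.24 and 1.60, power would be 89% and 80%. This stands as a qualification, although 360 is the protocol's own basis and 400 its maximum enrolment. The limit also moves with the formula, from 1.02 (continuity-corrected) to 1.09 (unpooled), with 1.05 on the log risk-ratio scale.

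Nothing in the documents shows that the design effect exceeds 1.08. Blocking on expected prescribing and adjustment for prior hospitalisation could recover some precision. Both points stand, and the magnitudes here are conditional for that reason.

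For ED visits the protocol openly reports 67–71%. The outcome also includes urgent care, so the true rate may be higher: at an assumed 0.065 per month, power at 360 per arm is 92%, and 86% at DE 1.24. The ED design effects are borrowed from the illustration for antipsychotic use. So the ED shortfall is uncertain, but the omission is not.

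Finally, the 89% vs 95% conflict is unrelated to clustering. That is so, and it is kept separate above; it concerns the same power text and needs correcting there.

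**Conclusion.** The concern holds. The power figures describe an individually randomised trial with independent patients and Poisson counts, not the prescriber-randomised design and GEE analysis that are planned. Any positive within-prescriber correlation lowers them. By how much cannot be determined from the documents, because the ICC and cluster sizes are absent; the values used for m, CV, ICC and k are assumptions.

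Within that limit, the 10-point claim is robust at 95% control use, moderately so at 90%, and at 85% tolerates almost no clustering on the protocol's 360 per arm. The ED test starts at 67% at the base rate and has no margin for clustering or overdispersion.

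The conflict over 89% vs 95% needs no assumption about clustering. Power over 95% is not attainable at the stated sample size, even with 400 per arm and independent patients.

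**What to change.** - Recompute the power text and table in Protocol section 8.2.1 over a declared range of design effects, DE = 1 + [(1 + CV²)m − 1]·ICC. Take m and CV from the prescribing counts already gathered at each site to form the randomisation blocks, and the ICC from the pilot or a stated range.
- Use the smaller within-subgroup cluster sizes for the subgroup rows.
- Use an overdispersed variance, as well as a design effect, for the ED non-inferiority power.
- Replace the two conflicting powers for 89% vs 95% with one reconciled figure, and state the method behind it.
- Say in sections 8.2.1 and 8.3 that the powers are conservative with respect to disenrolment only.

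The cost is a recalculated table and a few lines of text. Sample size, conduct and analysis stay as they are. The stated powers will look less favourable, and the ED test weaker than the 67–71% now given.

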Patient enrollment in the study occurs when a provider writes a qualifying antipsychotic prescription for an eligible adolescent patient or enters a patient reported medication (these two actions are indistinguishable in Epic). (Eligibility is confirmed by study staff following enrollment.) Follow-up time after enrollment extends for 6 months (181 days). Some patients will not remain enrolled in the health plan for a full six months, censoring follow-up, and the number of days covered in the health plan post-study enrollment should be recorded. If patients have a health care plan enrollment gap that is less than 45 days, they will be considered as having continuous enrollment in the study (i.e. not loss to follow up). For example, if a patient has a gap in their healthcare plan enrollment for less than 45 days during the study, this patient will be considered to have continuous enrollment. However, if there is an enrollment gap in their healthcare plan for at least 45 days, the patient will be disenrolled from the study at the healthcare plan disenrollment day. Note that, since patients do not have to be enrolled with a specific health care plan to be seen at NCH, we will assume a full follow up time of 6 months (181 days). Follow-up time should be indicated in the analytic dataset for all enrolled patients.

Analysis

Primary analysis I

Our primary analysis examines the percentage of patients taking antipsychotic medications (measured by provider medication orders) at 6 months post enrollment

Descriptive analysis will summarize **the percent of patients observed to be using AP at 6 months**, defined by presence of days' supply AP ≥ 181 days or medication in hand at 6 months. For example, if a patient has a 30-day supply order on or after 151 days post-enrollment, that patient has AP medication "in hand" at 6 months. Note: a patient does not have to have ≥ 181 days' total supply during the study to have medication in hand at 6 months. We will not adjust for loss to follow-up or disenrollment for this outcome definition. Patients who do not have prescription fill information up to 6 months post-baseline due to health plan disenrollment will have AP use observed at 6 months if they have AP orders after disenrollment that is ≥ 181 days. For example, if a patient disenrolls at day 160 and has a AP order (30 days' supply) after disenrollment, they have medication "in hand" at 6 months

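### The protocol's power was not re-derived for the SAP's first primary analysis, which keeps disenrolled patients in and counts those without supply reaching day 181 as non-users

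*Protocol*

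**What the plan says.** **Protocol, section 8.2.1 (power).** The protocol expects 400 patients per arm, with 360 per arm still enrolled at 6 months (also section 8.1). It claims "We have over 90% power to detect a 10% reduction in antipsychotic use at 6 months for patients in the intervention arm". This claim is tied to three assumed control rates: 85%, 90% and 95%. The power table uses 360 per arm and gives >99%, 97% and 92% for 95 vs 85, 90 vs 80 and 85 vs 75. For 95 vs 89 the table gives 80%, while the text claims over 95% for a 6% "reduction in the percent of participants with any order for antipsychotic medications at 6 months". The paragraph that introduces the table concludes: "In summary, at a range of percentages of participants with any antipsychotic use in the control arm, we will have excellent power".

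**Protocol, sections 8.2.1 and 8.3 (loss).** The planned analysis is Poisson regression with an offset for follow-up time. On that footing the protocol says: "Because our power calculations are based on excluding all individuals lost-to-follow-up due to disenrollment, these estimates are conservative". Section 8.3 repeats the claim.

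**SAP, Primary analysis I.** The outcome is binary: at least 181 days' supply, or medication in hand at 6 months. On leavers it says: "We will not adjust for loss to follow-up or disenrollment for this outcome definition". An order placed after disenrollment counts if its supply reaches day 181. Patients at Nationwide Children's Hospital (NCH) are given the full 181 days. The model is logistic GEE with no offset. The SAP contains no power calculation.

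**The concern.** The power calculation and the analysis treat the same 10% of patients in opposite ways. The protocol drops them and presents this as a worst case. The SAP keeps them. Those with no recorded supply reaching day 181 become zeros in both arms, which shrinks the difference and moves the control rate away from 95%, where the binomial variance is larger. Losing 40 patients per arm from the denominator costs less power than carrying them as zeros, so exclusion is not the conservative choice for this outcome.

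The control rate is a second gap. Neither document explains why 85% to 95% should apply to supply in hand at day 181 in a new treatment episode.

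What is at stake is how a null result would be read. The protocol names a 10-point minimal clinically important difference and says the trial is very likely to detect it. If power for the analysis actually run is nearer 81% to 90%, a non-significant result says less than the protocol implies.

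**Working it through.** **Inputs**
- Alpha: "Assuming a $P < 0.05$ alpha level" (protocol 8.2.1). The SAP's test is two-sided on a 95% CI: "We will reject the null hypothesis if the lower bound of the 95% CI is above 1", or if the upper bound is below 1. So z = 1.96.
- Enrolled 400 per arm, 10% lost, 360 retained (protocol 8.1).
- Control rates 95%, 90%, 85%; effect 10 points absolute (power table).
- Independence between patients. No intraclass correlation or design effect is given for power.

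**Formula** (two proportions, pooled variance under the null), with p̄ = (p₁+p₂)/2:

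Power = Φ{ [ |p₁−p₂| − 1.96·√(2p̄(1−p̄)/n) ] / √( [p₁(1−p₁)+p₂(1−p₂)]/n ) }

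**Step 1. The plan's own figures, 360 per arm, leavers excluded**

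| Control vs intervention | Computed | Power table | Text |
|---|---|---|---|
| 95 vs 85 | 99.5% | >99% | over 90% |
| 90 vs 80 | 96.5% | 97% | over 90% |
| 85 vs 75 | 92.0% | 92% | over 90% |
| 95 vs 89 | 84.5% | 80% | over 95% |

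Example, 85 vs 75: p̄ = 0.80; null SE = √(2×0.80×0.20/360) = 0.02981; alternative SE = √((0.1275+0.1875)/360) = 0.02958; (0.10 − 1.96×0.02981)/0.02958 = 1.405; Φ = 92.0%.

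The 10-point figures reproduce. The 6-point figures do not agree with each other. A continuity correction gives 80.9% at 360 per arm, close to the table. The formula gives 88.0% even with all 400 per arm, so the text's figure is not reached.

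**Step 2. The SAP's handling of leavers, 400 per arm, same underlying rates**

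Let s be the share of leavers with no supply reaching day 181. The observed rate is p × (1 − 0.10s). For s = 1 both rates are multiplied by 0.90; for s = 0.5, by 0.95. The documents do not give s, so it is an assumption, taken as equal in both arms.

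| Underlying rates | Observed, s = 1 | Power, s = 1 | Observed, s = 0.5 | Power, s = 0.5 |
|---|---|---|---|---|
| 95 vs 85 | 85.5 vs 76.5 | 90.2% | 90.25 vs 80.75 | 96.9% |
| 90 vs 80 | 81.0 vs 72.0 | 85.3% | 85.5 vs 76.0 | 92.8% |
| 85 vs 75 | 76.5 vs 67.5 | 81.0% | 80.75 vs 71.25 | 88.4% |
| 95 vs 89 | 85.5 vs 80.1 | 52.5% | 90.25 vs 84.55 | 68.1% |

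Example, 85 vs 75 with s = 1: p̄ = 0.72; null SE = √(2×0.72×0.28/400) = 0.03175; alternative SE = √((0.179775+0.219375)/400) = 0.03159; (0.09 − 1.96×0.03175)/0.03159 = 0.879; Φ = 81.0%.

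For 10 points at s = 0.25 (rates × 0.975), power is 98.8%, 95.7% and 91.6%, so all three rows stay above 90%.

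**Step 3. If the day-181 control rate itself were lower**

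No document gives this rate; the values below are assumptions. Here the 10 points are measured on the SAP outcome among all 400 per arm, so leavers are already inside the rate.

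| Control rate on SAP outcome | Power, 10 points, 400 per arm |
|---|---|
| 80% | 90.6% |
| 70% | 84.4% |
| 60% | 81.3% |
| 50% | 81.3% |

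Power falls below 90% once the control rate is under about 79%.

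**The case against.** The strongest reply is that the quoted sentence is conditional and correct. It names its control rates, and at those rates with 360 per arm the figures reproduce. That stands: this is an unsupported power assumption, not an arithmetic error, apart from the separate conflict over the 6-point reduction.

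A reader might infer that power was computed for an any-order measure and that the SAP then switched endpoint. The documents do not show this. The protocol's wording is mixed: one sentence speaks of any order, but the power claim speaks of use at 6 months and the table caption of taking medication at 6 months, which is close to the SAP's name for the outcome.

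A reader might also infer that the SAP scores all leavers as non-users. It does not. Orders after disenrollment count when supply reaches day 181, and the SAP gives such an example. Gaps under 45 days are not disenrollment, and NCH has no leavers by assumption. So s = 1 is the worst case, and even there the 95% row stays just above 90%.

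The scaled rates in step 2 also correspond to a 9-point observed difference (9.5 points at s = 0.5). A full 10 points on the SAP outcome at observed control rates of 85.5%, 81.0% and 76.5% has about 95%, 91% and 88% power. This is fair, and it shows that the restated power must say on which scale the 10 points are measured.

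Finally, the SAP was last updated in December 2021, after the contract phase was due to end in June 2021. Restating power cannot alter the design, and the confidence interval carries the inference. That limits the severity but does not make the stated power true of this analysis.

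**Conclusion.** The concern holds in a limited form. Power was never re-derived for the SAP's Primary analysis I. Using the plan's own control rates and 10% loss, power for a 10-point reduction is 81.0% to 90.2% if all leavers score 0 and 88.4% to 96.9% if half do. The claim of conservatism therefore does not carry over, and power above 90% at all three control rates is not assured. For 95 vs 89, power is 52.5% or 68.1%, against stated figures of 80% and over 95% that cannot both be right.

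These results assume a two-sided 0.05 test, independence, equal loss in both arms and a stated share of leavers scoring 0. Positive within-provider correlation would lower them.

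It would go too far to say that the trial lacks 90% power for 10 points. If about a quarter or fewer of the leavers score 0, all three rows stay above 90%. Nor do the documents support any particular day-181 control rate below 85%; rates of 50% to 80% are illustrations only. The point merits correction but ranks below the changes that must be made, because the test, outcome and decision rule are unaffected.

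**What to change.** In protocol section 8.2.1, restate power for the SAP outcome among all 400 per arm. Tabulate it over a range of day-181 control rates and over the share of leavers scoring 0 (for example a quarter, a half and all), label both as assumptions, and state whether the 10 points are on the underlying or the observed scale. Remove the claim that the estimates are conservative in sections 8.2.1 and 8.3, and remove the unqualified claims of over 90% and excellent power. Replace the text's figure of over 95% for the 6-point reduction with the recomputed one, and make text and table agree.

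The cost is one recomputed table and some rewording. The sample size and analysis do not change. The downside is a less favourable stated power.
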